Sample size considerations: Assessing 70 students per arm (total n=140) that have completed the program and follow up would provide sufficient data on the full RCT protocol across multiple campuses as well as estimates of intervention effects. Assuming a conservative retention rate of 70% for the three-month post-intervention follow up, we would need to enroll 200 participants at baseline. While we do not anticipate having sufficient power to detect statistically and clinically significant results, we have provided preliminary sample size calculations for our outcomes of interest. We estimated within-subject correlations to be between 0.2 and 0.6 between baseline and follow-up assessments.

Alcohol use (Number of drinking days, number of binge drinking days): Assuming a within-person correlation of 0.4 in alcohol use between baseline and follow up assessment, analyzing 70 students per arm (total n=140) would provide 80% power at $\alpha=0.05$ to detect a standardized difference of 0.395 between intervention and control. This translates to a 2-day greater reduction (SD=5.1 days) in number of drinking days in the past 30 days compared to a reduction seen with the control arm program. Given initials results of the control arm program, this would bring the total change needed to 3 fewer drinking days in the past 30 days from baseline

(150% greater efficacy compared to control program messaging). Assuming a 1-day greater decrease is possible with this intervention (2 days overall), 410 participants would need to be enrolled per arm (820 total), given 30% attrition.

SV Harm Reduction Strategy Use: Estimating a baseline prevalence of using at least one strategy at 25%, We believe a meaningful increase in any use is 30%. To achieve 80% power at an $\alpha=0.05$, and assuming a within-subject correlation of 0.4 between baseline and follow-up assessment, we would need 876 participants in each arm at follow-up; with 30% attrition, we would need to enroll over 2,500 total participants, at baseline. This sample sizes, however, are beyond the scope of the project. We believe enrolling 200 at baseline is feasible, providing 80% power at $\alpha=0.05$ to detect a 75% increase in any use of SV harm reduction strategies after accounting for attrition.

References

2. Strauss A. *Qualitative Analysis for Social Scientists*. New York: Cambridge University Press; 1987.

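### Does the SAP measure its meaningful 30% increase and its detectable 75% increase in harm reduction strategy use on different scales, and does it matter?

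*SAP*

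**What the plan says.** The figures are in the SAP, Sample size considerations, paragraph on SV Harm Reduction Strategy Use. The starting point is "Estimating a baseline prevalence of using at least one strategy at 25" per cent. The next clause is "We believe a meaningful increase in any use is 30" per cent. With 80% power, alpha 0.05 and "assuming a within-subject correlation of 0.4 between baseline and follow-up assessment", the SAP concludes that "we would need 876 participants in each arm at follow-up" and, allowing for 30% attrition, that "we would need to enroll over 2,500 total participants, at baseline". It calls this out of reach for the project. It then says that enrolling 200 gives 80% power "to detect a 75% increase in any use of SV harm reduction strategies" after attrition.

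Neither percentage comes with an end proportion, and no formula is named. The preceding paragraph, on alcohol use, gives two figures that help to identify the method: 70 per arm is enough "to detect a standardized difference of 0.395 between intervention and control", and for a 1-day difference "410 participants would need to be enrolled per arm (820 total), given 30% attrition".

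**The concern.** Two percentages in one short paragraph are both called an increase in any use, so a reader will compare them directly: the meaningful effect is 30%, and the pilot can detect 75%, or 2.5 times as much. If the 75% is relative (25% to 43.75%), the same scale makes the 30% a rise to 32.5%, or 7.5 points. But 876 per arm is too many for 7.5 points under the usual adjustments at a correlation of 0.4. It fits a 5-point difference. On a common relative scale the comparison is 75% against 20%, a ratio of 3.75.

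Strategy use is one of the three outcomes under Primary Outcomes in the SAP, and this sentence is the only statement of what effect on it would be meaningful. Someone planning the larger study could take the target as 7.5 points when the arithmetic used 5.

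**Working it through.** **Inputs.** From the SAP: control proportion 0.25, power 80%, alpha 0.05, correlation r = 0.4, 70 analysed per arm, attrition 30%. Assumed: a two-sided test (the SAP says two-sided only for the later study) and the pooled normal-approximation formula

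n = [1.960·√(2p̄(1−p̄)) + 0.842·√(p₁(1−p₁) + p₂(1−p₂))]² / (p₂−p₁)² per arm, where p̄ is the mean of p₁ and p₂.

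**Before any allowance for correlation**

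| Comparison | Reading | n per arm |
|---|---|---|
| 25% vs 30% | 30% as a level | 1250.7 |
| 25% vs 32.5% | 30% as a relative rise | 570.5 |
| 25% vs 55% | 30% as points | 40.7 |
| 25% vs 43.75% | 75% as a relative rise | 99.5 |
| 25% vs 75% | 75% as a level | 14.5 |

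**The correlation factor implied by each printed figure**

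- Strategy use, 876 for 25% vs 30%: 876/1250.7 = 0.700.
- Strategy use, 70 for 25% vs 43.75%: 70/99.5 = 0.703.
- Alcohol, 0.395 SD at 70 per arm: 0.395² × 70 / (2 × 2.8016²) = 0.696.
- Alcohol, 1 day with SD 5.1: 410 × 0.7 = 287 retained per arm, and 287 × (1/5.1)² / (2 × 2.8016²) = 0.703.

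All four are about 0.70, which equals (1+r)/2 at r = 0.4.

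**The plan's figures reproduced with 0.70**

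- 1250.7 × 0.70 = 875.5, so 876 per arm.
- 876/0.7 = 1251.4, so 1,252 per arm and 2,504 in total, which is over 2,500.
- 99.5 × 0.70 = 69.7, so 70 per arm. Solved the other way, 70 per arm detects 25% to 43.7%, a 74.8% relative rise.

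**The other readings with 0.70**

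- 30% as a relative rise: 570.5 × 0.70 = 399.3, about 400 per arm. Reaching 876 would need a factor of 876/570.5 = 1.536. At r = 0.4 other common factors give 479 (1−r² = 0.84) and 685 (2(1−r) = 1.2).
- 30% as points: about 29 per arm.
- 75% as a level: about 11 per arm. An added 75 points would mean 100% use.

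**A check that does not need the factor.** Any factor common to both sample sizes cancels in their ratio. The printed ratio is 876/70 = 12.5. A level of 30% with a relative 75% gives 1250.7/99.5 = 12.6. Both read as relative gives 570.5/99.5 = 5.7.

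**What depends on the 30%.** The 200 follows from 140 completers at 70% retention: 140/0.7 = 200. It uses no effect size. Under the relative reading, enrolment would be 400/0.7, or 572 per arm and 1,144 in total. That is still well over five times 200, so the conclusion that the target is out of reach is the same.

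**The case for a change.** The best case for acting is that the ambiguity is real and cheap to remove. The reader has to work back from 876 to learn that the target is 5 points, and the same noun a few lines later means a relative change. On the SAP's own method the two readings differ by a factor of 2.2 in sample size (876 against about 400 per arm), and the pilot exists to inform a larger trial. Quoting start and end proportions would settle it in one line.

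The observation stands: the scales differ and the end proportions are missing. The consequence does not follow. The Analysis sections of both documents size the later study from the effects estimated in the pilot, so the 30% is not carried forward, and no decision rule uses it. Straight after a baseline of 25%, an increase given as 30% is naturally taken as a rise to 30%, and anyone who checks 876 arrives there.

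Nor can back-calculation settle beyond doubt what the sponsor regards as meaningful. The SAP names no formula, and 0.70 is also the retention proportion. Within the SAP's wider correlation range of 0.2 to 0.6, a change-score comparison of 25% vs 32.5% at r = 0.2, with unpooled variances and a flat control arm, needs about 873 per arm. That reading fits poorly, because the sentence states 0.4 and the same method would need about 145 per arm, not 70, for the 75% rise. It still argues against writing 25% to 30% into the plan on the sponsor's behalf.

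**Conclusion.** The wording is loose and the numbers are sound. The 30% is best read as a level (5 points, 20% relative) and the 75% as a relative rise (18.75 points). On those readings 876 per arm, over 2,500 enrolled and the detectable effect at 70 per arm all reproduce to rounding. This rests on a two-sided test, the normal approximation and an inferred factor of about 0.70. The finding that the scales differ needs only that one common factor was used, since 12.5 matches 12.6 and not 5.7.

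No change follows. A rewording would keep every printed sample size and would alter nothing that the pilot does or can conclude: its size comes from retention, the Sample size considerations sections of both documents disclaim adequate power, and the later study takes its effect sizes from the data. Planners of that study can recover the intended proportions from the printed figures, as above, or ask the sponsor.
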